## Statistical Analysis Plan

Protocol Number: 274137

	
Data related to PM2.5 will be generated from two PurpleAir monitors installed in each participating home in most cases. Some smaller homes will have only one PurpleAir monitor installed. The data will be collected by a research team (third party) at the University of Montana (UM) every day during the study or follow-up period for a total of 26 weeks (24 weeks after intervention). The UM team will then convert the original data into PM2.5 levels using an EPA-defined formula, after data cleaning, quality assurance (QA) and quality control (QC). The UM team has developed a protocol of procedures for downloading, QA/QC checking, cleaning, computing, and saving PurpleAir data to ensure high quality PM2.5 measurements. An R script has been developed, tested and saved in a server of the CPHR at UM.

Study Variables 

➤ Demographic characteristics

➤ Environmental factors

➤ Medical history

	
Description
 

➤ Please see Table 2 in section 6.4 for variable information.

## **6. Analysis**

### **6.1. General Considerations**

#### **Timeline for final statistical analysis:**

The final analysis will be performed after data collection and entry is complete on 228 participants and bioinformatics team has completed the data transfer to the study biostatistician.

#### **Statistical Software:**

SAS software version 9.4 (SAS Institute, 2016) and R software version 4.4.1 (R Core Team 2021) will be used in the analysis.

#### **Statistical Significance and Precision:**

A p-value less than 0.05 is considered to be statistically significant.

[figure not shown]
### **6.2. Data Screening**

Summary/descriptive tables and/or graphical tools will be used to describe the distribution for continuous variables and proportions for categorical variables to ensure the levels are captured appropriately. The distribution of primary and secondary endpoints will be inspected for normal assumptions using the histogram plots. A transformation variable may be used in the parametric models to ensure the assumption of normality is met.

### **6.3. Subject Disposition**

The flow of participants through the study will be displayed in a CONSORT flow diagram (see Figure 1 below for the template that will be used)

#### **Figure 1. Consort flowchart template for subject disposition**

#### 6.4. Participant Demographics and Baseline Variables

The participant demographics and baseline variables are summarized in Table 2. The baseline variables were collected after randomization but prior to intervention initiation.

**Table 2. Summary of Baseline Characteristics and Covariates**

Sites	Variable	All N participants	Intervention Group	Control Group
Infant demographics				
Site 1	Infant's Age at initial hospitalization for bronchiolitis (in months), mean (SD)			

Gestational age at birth (in weeks), mean (SD)
Infant's Sex, N (%)
Infant's Race, N (%)
Infant's Ethnicity, N (%)
Rurality (RUCA code), N (%)
Parent/caregiver/legal guardian education, N (%)

---

**Environmental factors**

---

Wood-burning stove ever used in the home (primary place of residence), N (%)
Central air conditioning in the home (primary place of residence), N (%)
Type of stove is used, N (%)
A fume hood (or range hood) is above the primary cooking stove, N (%)
Use fume hood while cooking, N (%)
Has plumbed (running) water in the home, N (%)
Furry pets in the home, N (%)
Infant attends a child care center with at least 2 other infants / children who are not members of the infant's household, N (%)
Number of people live in the home (primary place of residence), (IQR)
Number of other children are living in the home (primary place of residence), (IQR)
Number of the other children living in the home attend daycare or school, (IQR)

---

**Medical history**

---

Viral test results (first hospital admission for bronchiolitis), if available, per standard of care testing, N (%)
---

Highest level of respiratory support during bronchiolitis admission, N (%)
Infant ever received systemic corticosteroids during hospitalization for bronchiolitis, N (%)
Previous history of wheezing with colds or other illnesses (besides this hospitalization), N (%)
History of asthma in the infant's parents or siblings, N (%)
Child has eczema or atopic dermatitis based on healthcare provider, N (%)
Child has been on chronic asthma medications at home any time before they were hospitalized, N (%)
Child ever used asthma medications with other breathing illnesses (such as colds, wheezing, or asthma) in the past (before this hospitalization), N (%)
Site 2
Etc...

## 6.5. Data Summary and Visualization

All numerical variables will be summarized using mean  $\pm$  standard deviation and median (minimum, maximum). All categorical variables will be summarized using frequency (%). The variables will be summarized using descriptive statistics overall and stratified by intervention groups (HEPA filtration versus control) as well as by sites. The variables will be compared between groups (HEPA filtration vs. control) using two sample t-tests; or Wilcoxon rank sum tests if they are numerical variables, and Chi-square tests or Fisher's exact tests if they are categorical variables. The choice of a t-test or a Wilcoxon rank sum test will depend on the empirical distribution of the tested numerical variable. The choice of a Chi-square test or a Fisher's exact test will depend on the sample size used in the test.

Under the study design of stratified randomization, it is unlikely to expect any significant association between baseline characteristics and the intervention effect. However, some of the

baseline characteristics could be associated with the endpoints. For a candidate covariate used in multivariate analyses, its correlation to the primary endpoint, or a secondary endpoint will be assessed using a Pearson's correlation coefficient or a Spearman's correlation coefficient when it is a numerical variable. When the covariate is categorical, its association to the primary endpoint, or each of the secondary endpoints will be assessed using an ANOVA model, or a Kruskal-Wallis test. A variable that is associated with the intervention and primary endpoint and secondary endpoints or the association is mentioned in the previous literature will be considered as the adjusting (controlling) covariate and will be added as adjusting independent variable in the statistical models proposed for primary and secondary analyses.

## **6.6. Efficacy Analysis**

### **6.6.1. Primary Efficacy Analysis**

For the primary efficacy measure, we will test the following null hypothesis:

Null hypothesis: Mean of SFDs in the HEPA filtration home intervention group will not differ from the mean of SFDs in the control group.

vs

[figure not shown]
Alternative hypothesis: Mean of SFDs in the HEPA filtration home intervention group is larger than the mean of SFDs in the control group.

The primary endpoint is the number of caregiver-reported symptom-free days (SFD) over 24 weeks following activation of filtration (SFD is defined as a 24-hour period without coughing, wheezing, or trouble breathing). The SFD is observed through a survey each week. The survey is completed on each Sunday, and the symptom-free days are recorded from Sunday in the last week to Saturday, or the day before the survey date. The total SFDs range from 0 to 168 days (7\*24 weeks) assuming no missing data. Complete case analysis is considered as the primary analysis. For situations of missing surveys, see Handling Missing Data section 6.8.

Figure 2 shows the flowchart of surveys of symptom-free days. If a caregiver replies a "No" to the question "During the last full week (Sunday through Saturday), did your child have any coughing, wheezing, or trouble breathing?", then the recorded SFDs in this week are seven. On the other hand, if the caregiver reports a "Yes" in the previous question, and answers a "Yes" in any of the following categories "Daytime Cough", "Daytime Wheeze", "Daytime Trouble

Breathing", and "Nighttime Awakening due to Cough" for all seven days in a week, then the SFD of the survey week will be zero.

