9.4.2 ANALYSIS OF THE PRIMARY EFFICACY ENDPOINT

- **Primary Objective:** To test the efficacy of a HEPA filtration unit home intervention, relative to the control arm, with respect to respiratory symptom burden (as measured by symptom-free days; SFD) over 24 weeks following activation of filtration.
- **Primary Endpoint:** Number of caregiver-reported SFDs over 24 weeks following activation of filtration (SFD defined as a 24-hour period without coughing, wheezing, or trouble breathing)
- **Statistical Hypothesis:** Mean of SFDs in the HEPA filtration home intervention group is larger than mean of SFDs in the control group. The hypothesis testing is the comparison of superiority.
- **Statistical Procedures:** The hypothesis will be tested using a mixed effect model after accounting for within cluster correlation. The model uses the primary endpoint as the dependent variable, and the intervention effect (intervention vs. control) as the independent variable or the fixed effect with site as a random effect.
- **Missing Data:** The primary endpoint will be imputed if there is any missing observation in the ITT. The statistician will assess the missing patterns to determine if the cause of missing is missing at random (MAR), missing completely at random (MCAR), or missing not at random (MNAR). Imputation methods such as multiple imputation (MI) methods and pattern-mixture methods will be used in imputation and analyses.

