## **4. Analysis Populations**

### **4.1. Intent-to-Treat Population**

Intent-to-Treat (ITT) Population: The ITT population will include all participants who are randomized to either HEPA filtration (intervention group) or inactive filter unit (control group).

The primary set of analyses for this study will be based on ITT population. A separate analysis will be done with the Per-Protocol population.

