### **HANDLING MISSING DATA**

[figure not shown]
The patterns of missing will be inspected to determine if the missing data are missing completely at random (MCAR), missing at random (MAR), or missing not at random (MNAR). Under the scenario of MCAR, the analysis will be performed using complete data or mean imputation.

When MAR is assumed, a multiple imputation method will be used to impute missing data based on the relationships between the missing data and other observed variables. If the missing data are MNAR, then pattern mixture models will be used in imputation and inference (Little & Wang, 1996).

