#### **Primary endpoint of SFDs:**

The complete case analysis may underestimate the total SFDs since all missing values will not be considered as SFDs. We will use both simple imputation and multiple imputation at the weekly level for missing values of SFDs and compare the results with a complete case analysis (Figure 3).

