#### Step 2 option 2: Multiple imputation at the weekly level

The simple imputation based on weekly mean SFDs may result in biased estimates if the data are missing for more than 10% of the participants or have a large proportion of missing weeks (Eekhout et al., 2014). After evaluation of the missing proportion and pattern, multiple imputations could be used. If the caregiver fails to submit the weekly survey or no information was provided for seven days of the week, the SFDs of the week will be coded as missing. The multiple imputation will be conducted at a weekly level. The number of missing observations ranges from 0 to 24 weeks. Multiple imputation will be used to predict how many SFDs per week by the selected observed weeks based on 1) the correlations between the missing weeks and other observed weeks; and 2) the duration of the bronchiolitis symptoms (number of weeks to be included). Multivariate Imputation by Chained Equations (MICE) R package (van Buuren & Groothuis-Oudshoorn, 2011) or MI procedure in SAS software (SAS Institute Inc., 2015) will be used. The imputation process will be repeated for at least 10 times at the weekly level (Stuart et al., 2009), after which the total SFDs across 24 weeks will be calculated by adding up the observed and imputed weekly SFDs for every imputed data set. Each of the imputed data sets will be analyzed using a mixed effect model, and the parameter estimates will be combined from all analyzed data sets at the pooling phase.

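### The SAP makes complete case analysis of total symptom-free days primary, against the protocol's rule to impute in the ITT, and its own text implies that missing weeks count as zero

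*SAP*

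**What the plan says.** Three places set the rule for a missing primary endpoint.

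- **Protocol 9.4.2:** "The primary endpoint will be imputed if there is any missing observation in the ITT". It names multiple imputation and pattern-mixture methods as examples.
- **SAP 6.6.1:** "Complete case analysis is considered as the primary analysis". It sends missing surveys to section 6.8.
- **SAP 6.8, Handling Missing Data:** the mechanism judged to apply selects the method. Complete data or mean imputation go with missing completely at random (MCAR), and pattern mixture with missing not at random. For the case in between: "When MAR is assumed, a multiple imputation method will be used to impute missing data".

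On what complete case means, SAP 6.8 offers one sentence: "The complete case analysis may underestimate the total SFDs since all missing values will not be considered as SFDs". It refers to Figure 3, which is not available in the text.

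SAP 6.8, Step 2 option 2, describes weekly multiple imputation, but conditionally: "After evaluation of the missing proportion and pattern, multiple imputations could be used". The 24-week total "will be calculated by adding up the observed and imputed weekly SFDs for every imputed data set". SAP 6.6.1 models the total as a Poisson or negative binomial count with a log link and states no offset. SAP 4.1 adds: "The primary set of analyses for this study will be based on ITT population". SAP section 7, where changes from the protocol must be described and justified, lists none.

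**The concern.** The analysis ranked first in the SAP is not the one the protocol requires, and the SAP itself says that it may understate the endpoint. If unsubmitted weeks add zero, a child's total partly measures how many surveys the family returned. A child who drops out at week 6 looks like a child who was symptomatic from week 7 onward. That shrinks a true difference, adds variance, and can move the arms apart if survey completion differs between them.

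Missing weeks are foreseen. SAP 3.4 cites increased dropout during follow-up and plans for 14% attrition, Protocol 9.2 plans for 16%, and SAP 6.8 lists unsubmitted surveys as the first source of missing data.

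**Working it through.** **Inputs from Protocol 9.2 and SAP 3.4.** Control mean 98 of 168 days, difference 20, SD 43, 98 per arm, 90% power, two-sample t-test. Protocol 9.4.1 sets two-sided 0.05. Attrition is 16% (protocol), 14% (SAP, 114 per arm) or originally 10% (SAP, 109 per arm).

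**The plan's own figure.** The effect size is 20/43 = 0.465. With 98 per arm the noncentral t gives power 0.8997, so the stated 90% reproduces.

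**Assumptions added here.** A share *d* of each arm drops out, with completed weeks *k* uniform on 0–23. Each child has a constant rate of symptom-free days, and rates vary between children so that the full 168-day total has SD 43. There is no site effect.

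**Sum of observed weeks: difference.** The mean of *k* among dropouts is 11.5, so the missing fraction is *d* × 12.5/24. The difference becomes 20 × (1 − *d* × 12.5/24).

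**Sum of observed weeks: SD.** With *m* = mean/168, the between-child variance of the rate is *v* = (43² − 168·*m*(1 − *m*))/(168 × 167). For control this is (1849 − 40.8)/28056 = 0.0644. A child observed for *n* = 7*k* days has mean *nm* and variance *nm*(1 − *m*) + *n*(*n* − 1)*v*. Mixing over *k* (probability 1 − *d* at 24, *d*/24 at each of 0–23) gives the SD. The table shows the root mean square of the two arms' SDs.

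| Dropout, n per arm | Difference (days) | SD | Power, raw sum |
|---|---|---|---|
| 10% of 109 | 20 × 0.948 = 19.0 | 45.9 | 86% |
| 14% of 114 | 20 × 0.927 = 18.5 | 46.8 | 85% |
| 16% of 114 | 20 × 0.917 = 18.3 | 47.2 | 83% |

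Simulation of the same set-up agrees: differences of 19.1, 18.6 and 18.4 days, and power of 86%, 84–85% and 82–83%. On the same data, totals scaled to observed days give 92–94%. Weekly multiple imputation gives 93%, 93% and 94%.

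**Sensitivity to timing and correlation.** At 16%, power for the raw sum is 74% if all dropout falls in weeks 0–11 and 92% if it falls in weeks 12–23. With weekly autocorrelation 0.9 it is 81% (against 93% with multiple imputation).

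**Model.** A negative binomial fit to the raw sum gives 64–70%. It gives only 87% with no dropout, so part of that loss comes from the model and is not charged to this point.

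**Type I error, both means 98, 114 per arm.** Equal 16% dropout gives 5.0%. At an assumed 20% control v 12% HEPA, expected totals are 98 × (1 − 0.20 × 12.5/24) = 87.8 and 98 × (1 − 0.12 × 12.5/24) = 91.9, a spurious 4.1 days. Rejection is about 10% by t-test and 4–5% by negative binomial. Multiple imputation holds 5%.

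**The other possible meaning: only children with all 24 surveys.** With 16% dropout, 114 × 0.84 = 96 per arm remain and power is 89% if nothing else is missing. The documents give no missed-survey rate. At assumed weekly rates of 1%, 2% and 5%:

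| Misses within a family | All 24 returned | Power |
|---|---|---|
| Independent (0.99²⁴, 0.98²⁴, 0.95²⁴) | 79%, 62%, 29% | about 80%, 70%, 40% |
| Clustered, assumed ICC 0.1 | 89%, 78%, 54% | 85%, 81%, 65% |
| Clustered, assumed ICC 0.3 | 94%, 88%, 73% | 87%, 85%, 78% |

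**The case against.** The strongest reply is that the SAP is not ambiguous about rank. Section 6.6.1 names complete case as primary, and 6.8 presents imputed findings beside it and compares them with it. Only the general mechanism paragraph in 6.8 pulls the other way, and it can be read as choosing among imputation methods. This stands as far as it goes: a reader might infer that the SAP leaves the primary result unnamed, and it does not. But a clear ranking does not remove the contradiction with Protocol 9.4.2, and showing imputed results alongside does not make them decide the trial.

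Three other stronger readings are tempting, and the documents do not support them.

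- **That the plan breaks ITT.** This follows only if complete case means all 24 surveys. The SAP's remark about understated totals fits children kept in with gaps. The steep power losses under the all-24 meaning also need independent misses, and the plan pays for each survey, sends repeated reminders and offers a telephone alternative.
- **That false positives are inflated.** This needs dropout that differs by arm. Even at 20% v 12% it appears with a t-test but not with the negative binomial, one of the SAP's two candidate models.
- **That the SAP's 10% warning contradicts its primary analysis.** The warning that results "may result in biased estimates if the data are missing for more than 10% of the participants" concerns simple imputation by weekly means and is the reason given for multiple imputation.

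Figure 3 may define the term. It could not reconcile 6.6.1 with the protocol. Nor does the text show whether the day-level imputation in Step 1 applies to the complete case analysis.

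**Conclusion.** The point holds. The SAP's primary analysis departs from Protocol 9.4.2 without a record in section 7, conflicts with the MCAR condition in SAP 6.8, and by the SAP's own account may understate the endpoint.

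On the meaning that the text favours, the cost is a difference cut from 20 to between about 18 and 19 days, and t-test power of about 83–86% where 90% was planned. That rests on the plan's means and SD, on 10–16% dropout spread uniformly over follow-up, and on 109 or 114 randomized per arm. The 228 in the protocol counts consents, so the randomized number may be smaller. The comparison figure of about 93% exceeds 90% because it uses all 109–114 children per arm, so the shortfall against plan is about 4 to 7 points.

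A lasting type I problem is not shown. The all-24 meaning would drop randomized children against SAP 4.1, but it is the less likely one and its cost cannot be fixed from the documents.

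**What to change.** - Make the weekly multiple imputation in SAP 6.8, Step 2 option 2, the primary analysis in all randomized participants, as a firm commitment. Include arm, site and observed weekly symptom-free days in the imputation model.
- Define complete case at child and week level and keep it as a sensitivity analysis. Scale any observed-data total by days observed, or give it an offset; do not use a raw sum.
- Commit to the pattern-mixture analysis, already named in both documents, as a sensitivity analysis however missingness is classified.
- Reconcile SAP 6.6.1 with 6.8 and record any remaining departure from the protocol in section 7, before outcomes are analysed by arm.

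This costs SAP wording only; no new data or methods are needed. The drawback is that the primary result then relies on missing at random, which is why the pattern-mixture analysis should be firm.

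Separate and minor: SAP 6.8 does not statistically impute healthcare visits in missed weeks, whereas Protocol 9.4.3 applies the primary endpoint's methods to secondary endpoints. Those two should also be reconciled.

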**Figure 2. Flowchart for weekly survey of symptom free days**

### Univariate Analysis

The primary endpoint will be measured as a count variable. The hypothesis will be tested using a generalized linear mixed model (GLMM) with a log link function. The Poisson or negative binomial distribution will be used based on statistical convergence and dispersion. The model uses the primary endpoint as the dependent variable, and the intervention effect (intervention vs. control) as the independent variable or the fixed effect with site as a random effect. We will calculate the point estimates (i.e., average SFDs) and their respective 95% CIs for each intervention group and for the difference in average SFDs between the intervention groups. Additionally, we will report the p-value of the difference in point estimates between intervention groups.

### Multivariable analysis

Potential confounders will be adjusted for the impact of intervention effect on the SFDs using a multivariable GLMM. We will calculate adjusted point estimates (i.e., average SFDs) and respective adjusted 95% CIs for each intervention group and for the difference in average SFDs between the intervention groups. We will also report the adjusted p-value of the difference in point estimates between intervention groups.

#### **6.6.2. Analysis of Secondary Endpoints**

##### **Secondary Endpoint 1: UHVS**

For the secondary endpoint measure, we will test the following null hypothesis:

Null hypothesis: Mean of counts of unscheduled healthcare visits for respiratory symptoms in the intervention group will not differ from the mean of counts of unscheduled healthcare visits for respiratory symptoms in the control group.

vs

Alternative hypothesis: Mean of counts of unscheduled healthcare visits for respiratory symptoms in the intervention group is smaller than mean of counts of unscheduled healthcare visits for respiratory symptoms in the control group.

Caregiver reported counts of unscheduled healthcare visits (UHV) from each of the metrics including 1) hospitalizations; 2) Emergency Department (ED) or Urgent Care (UC) visits; 3) other unscheduled medical visits for respiratory complaints (cough, wheeze, or trouble breathing); and 4) A sum of counts (or total counts) of all metrics.

The counts of hospitalizations, ED or UC visits, and other unscheduled medical visits will be obtained from the caregiver's weekly survey or adverse event forms. The total count is the aggregation of counts of all unscheduled healthcare visits described above.

